#### Sample size determination

---

*Include power calculations or provide justification for their absence (e.g., pilot/feasibility study).*

Sample size assumptions: For sample size calculations we assume the following: 1) all participants will be included based on their randomized assignment; 2) a two-sided type-I error probability of 0.05; 3) a cumulative attrition rate of at most 15%; 4) modest levels of intervention non-adherence and missing data, such that total missingness at six months post intervention will be at most 20%, leaving 114 participants with evaluable data at the end of follow-up, consistent with our experience in this population; and 5) analyses utilizing multiple imputation will have similar power to those using observed data, consistent with theory and

prior experience. We anticipate greater power in practice owing to data obtained from the multiple follow-up measurements.

**Aim-specific Analytic Plan and Power:** **Aim 1** will test the effect of tDCS on dual task costs to standing and walking. The mixed-effects regression approach described above will estimate mean differences between tDCS and sham outcomes at the end of intervention and at three and six months thereafter. We will test the hypothesis that post-intervention changes in outcomes differ between randomized arms, and will additionally estimate timepoint-specific differences between arms in order to assess duration of effects. These models will control for dual-task cost to serial subtraction performance (as a time-varying covariate) to isolate the costs to gait by adjusting for potential differences in task prioritization over time. Sensitivity assessments will stratify by sex to assess empirical evidence of sex-specific effects (see below). Association between model-based estimates of subject-specific intercepts and slopes (generated as random effects) will be examined to assess the degree to which change with time is associated with the average level of function denoted by each measurement. **Sample size estimates:** Prior experiences suggest that 1) inter-individual standard deviation of dual-task costs under either sham or intervention will be no greater than 20%, 2) serial measures of dual task costs express substantial within-participant correlation, in excess of 0.8, and 3) real tDCS intervention reduces dual task costs (Section 3.3.2.2). We assume conservatively that the proposed study will obtain serial correlation of at least 0.75. Assuming evaluable data on at least 57 participants per arm, the trial will provide **90% power to detect a mean difference of 8% between intervention and control arms** in a comparison of dual task costs at any time following cessation of intervention.

The trial will thus be well-powered to detect differences more subtle than the clinically-meaningful differences observed between those with and without a history of falls.  
43-50

We anticipate greater power attending application of the repeated-measures analysis to all post-intervention data. **Aim 2** will test tDCS effects on physical function as primarily expressed by SPPB. Change scores between 0.5-1.3 have been proposed as the minimum of clinical significance. We will again use the mixed-effects linear model. Based on prior trials and data in this population we expect that SPPB will have baseline standard deviation of 1.5 units and will exhibit high serial correlation over the repeated measurements in this design, as high as 0.9. Assuming a more conservative serial correlation of 0.75, simulation studies (50,000 replicated trials) indicate that the repeated measures design will obtain 92% power to detect a mean intervention-attributable effect on SPPB of 0.5 units. **Aim 3** will test the tDCS effect on executive function measured primarily by the TMT (i.e., TMTB-TMTA); simulation studies similarly indicate that we will achieve at least 90% power to detect standardized effects of the tDCS intervention of 0.35 or greater.

**Missing data:** To accommodate attrition and other sources of missingness, we will utilize the method of multiple imputation by chained equations. At least 50 replicates of each missing value will be generated for inclusion in analyses. This method accommodates clustering of repeated measures at the participant level. We have previously used these methods in trials of anabolic and exercise interventions in similar populations.

Sensitivity analyses: To determine robustness of results we will consider the potential for confounding or effect modification according to baseline age, sex, BMI, and other covariates listed in Section 3.3.7.3. These will be addressed in secondary exploratory and regression analyses in parallel to those described above.

Insurance of scientific rigor—attention to age and sex as biological variables: The trial design is cognizant of the potential influence of age and sex on results. Randomization will be stratified by participant-identified sex classification and this will be acknowledged in all analyses. Sensitivity analyses will also be conducted to address the potential for effect modification by age and these will be reported in publication.

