The observation that older adults with a history of falls exhibit exaggerated dual task costs suggests that they have a reduced capacity to activate the required brain regions needed to maintain performance in both tasks. Studies using fMRI, EEG and/or functional near-infrared spectroscopy (fNIRS) indicate, as expected, that standing and walking, especially when dual tasking, activate the prefrontal cortices—the primary brain regions giving rise to cognitive function. Studies using fNIRS to measure brain activation (i.e., relative increases in oxygenated hemoglobin levels) *during* standing and walking indicate that when

compared to normal conditions, standing or walking while performing a verbalized serial subtraction task increases prefrontal cortex activation within both hemispheres, *but particularly within the left hemisphere.* Several of these studies have further reported those who exhibit greater increases in left prefrontal activation when dual tasking exhibit lower dual task costs and better executive function.

fMRI evidence indicates that performing two cognitive tasks together—as compared to performing them separately—activates additional brain regions *specifically within the left dlPFC.* Moreover, the left dlPFC is particularly activated during performance of cognitive tasks that require both working memory and verbal processing. We thus contend that while the control of standing and walking likely calls upon the bilateral dlPFC and its connected neural networks, the left dlPFC is important to one's ability to safely stand and walk while completing cognitive tasks that require verbalization—an ability central to daily living activities.

***tDCS holds promise as a therapy to mitigate dual task costs to standing and walking, and improve other physical and cognitive outcomes on the causal pathway to falls, in older adults.*** tDCS modulates cortical excitability (i.e., the likelihood of neuronal firing) by inducing low amplitude current flow between two or more electrodes placed upon the scalp. The electric fields thus polarize neuronal populations and modulate cortical excitability. The electric fields generated by tDCS and their effects on brain tissue excitability depends upon electrode size, polarity and placement, as well as current amplitude and duration.

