Single-session tDCS: Twenty continuous minutes of tDCS increases brain excitability within target regions for at least 1 hour thereafter. When delivered with the participant at rest, tDCS with the anode (positive electrode) over the left dlPFC improves performance in cognitive tasks requiring attention, working memory decision making, and even dual tasking in younger adults. [name] and his team have demonstrated that when tested just after stimulation, 20 minutes of tDCS targeting the left dlPFC reduces dual task costs to the control of standing and walking in healthy younger adults, healthy older adults, and in older adults with slow gait and executive dysfunction

Multi-session tDCS: tDCS interventions targeting the left dlPFC have proven effective for the treatment of depression and chronic pain. Much less is known regarding the effects of tDCS intervention in older adults without major neurologic disease. Yet, our recent work suggests that a two-week, ten-session tDCS intervention targeting the left dlPFC reduces dual task costs to both gait and balance, and, over a two-week follow-up, improves performance in several tests of physical and cognitive function in older adults with slow gait and mild-to-moderate executive dysfunction.

**The proposed project is significant because it will systematically examine the effectiveness of a multi-session tDCS intervention targeting a critical brain region involved in dual task standing and walking in older adults who are vulnerable to falling.** We expect to demonstrate that a personalized, multi-session tDCS intervention designed to increase the excitability of the left dlPFC improves dual tasking and other important physical and cognitive outcomes in older adults. Moreover, this trial will establish the size and duration of tDCS-induced benefits, and quantify its associated biophysical metrics via current flow modeling (i.e., average electric field

on target; see Innovation Section below). Together, these discoveries will enable future studies to 1) use neuroimaging to identify the effects of tDCS on brain activation and its relationship to function, 2) optimize tDCS as a longer-term intervention by incorporating “maintenance” tDCS after the initial intervention, and 3) further establish tDCS as a stand-alone or adjunct fall prevention strategy.

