**Previous (non-clinical, pre-clinical or clinical) studies leading up to and supporting the proposed research**

---

***Single sessions of tDCS targeting the left dlPFC reduce dual task costs and improve mobility in multiple populations:*** In three separate but related studies, [name] studied healthy young adults ( $22 \pm 2$  yrs), relatively healthy older adults ( $69 \pm 5$  yrs), and older adults with slow gait and mild-to-moderate executive function ( $81 \pm 10$  yrs) (manuscript in press). All participants completed two visits. On each visit, standing and walking were assessed both with and without simultaneous performance of a serial subtraction cognitive task, just before and after a single 20-minute session of tDCS targeting the left dlPFC on one visit, and sham stimulation on the other visit, in random order. In all three cohorts, stimulation did not alter standing postural sway or walking speed under single task conditions. However, during dual tasking, real tDCS was associated with less postural sway speed and area when standing, and faster gait speed when walking ( $p < 0.01$ ). As a result, only real tDCS reduced the dual task cost (i.e., percent change from single to dual tasking) to these outcomes (sway speed:  $p < 0.1$ ; sway elliptical area:  $p < 0.02$ ; gait speed:  $p < 0.01$ ). Together, these data give us confidence that increasing prefrontal cortex excitability provides at least short-term benefit to dual task performance across individuals who range widely in both age and functional capacity.

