## Provide study objectives/aims/hypotheses

---

Our Overall Aim is to compare, in older adults with previous falls, the effects of a *personalized* tDCS intervention designed to target the left dlPFC on the dual task costs to standing and walking, and other physical and cognitive factors that are on the causal pathway to falls and important to everyday function. We will conduct a randomized, sham-controlled, double-blinded trial with assessments at baseline and post-intervention (immediate, 3-, 6-month follow-up) in 144 non-demented men and women (72 per arm) aged 65-85 years who report  $\geq 2$  non-syncopal falls within the previous year and are fearful of falling again, yet have no major neural or musculoskeletal disorders that explain their falls. The tDCS intervention will comprise 20, 20-minute sessions of tDCS over a 4-week period. Importantly, we will utilize current flow modeling from baseline structural MRIs to determine the tDCS electrode placement and stimulation parameters that optimize electrical current flow to the desired target within each participant's brain.

**Specific Aim 1:** To test, in older adult "fallers," the effects of tDCS intervention targeting the left dlPFC on the dual task costs to the control of standing and walking. Standing and walking will be assessed with and without a concurrent cognitive dual task (i.e., verbalized serial subtractions). Primary outcomes will be dual task costs to postural sway speed when standing, and gait speed when walking, as these are well-established measures of functional mobility that are associated with falls.

**Specific Aim 2:** To test, in older adult "fallers," the effects of tDCS intervention targeting the left dlPFC on metrics of physical function that have been linked to frontal executive networks and associated with fall risk. The primary outcome will be the Short Physical Performance Battery (SPPB). Secondary outcomes will include the Timed Up-and-Go (TUG) test of mobility, fear of falling, and habitual physical activity.

**2.0 Specific Aim 3:** To test, in older adult "fallers," the effects of tDCS intervention targeting the left dlPFC on cognitive functions that have been linked to frontal executive networks and associated with fall risk. The primary outcome will be executive function as measured by the Trail Making Test. Secondary outcomes will be derived from tests of processing speed, working memory and sustained attention.

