**Dual task performance:** Procedures will follow published recommendations that produce excellent test-retest reliability. We have used this paradigm within our research and laboratory for over ten years. Participants will complete three, 60-second trials in each of five conditions:

- Condition 1: Single task: seated cognitive task (see below for description).
- Condition 2: Single task: standing.
- Condition 3: Single task: walking.

- Condition 4: Dual task: standing with cognitive task.
- Condition 5: Dual task: walking with cognitive task.

All standing trials will be completed on a stationary force plate (Kistler, Inc) to record postural sway (i.e., center of pressure) fluctuations throughout the trial. Participants will stand barefoot with arms at their side and feet shoulder width apart. The feet will be traced on the first trial and this tracing will be used to ensure consistent foot place throughout the study. Participants will be instructed to focus their attention on an “X” marked on a wall in front of them at eye level and will be reminded to stand as still as possible before each trial. All walking trials will be completed around a 25m indoor track. Prior to testing, participants will be outfitted with wireless biosensors—each containing a triaxial accelerometer, goniometer and magnetometer—on the sternum, low back, wrists and ankles to record gait kinematics (Mobility Lab™, APDM Inc). Participants will be reminded to walk at their preferred, comfortable place prior to each walking trial.

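### The Aim 1 models condition on a post-randomisation variable that tDCS may itself change, and no Aim 1 model without it is described

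*Combined protocol and SAP*

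**What the plan says.** Specific Aim 1 (section 2.0, objectives) is to test "the effects of tDCS intervention targeting the left dlPFC on the dual task costs to the control of standing and walking". Its primary outcomes are the dual-task costs to sway speed and to gait speed.

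The overall approach in section 6.0 is a mixed-effects regression of the outcomes measured after the intervention and at three and six months, adjusted for the baseline outcome and sex. The Aim 1 paragraph under Sample size determination uses that approach to test the arm difference and estimate it at each timepoint. It then adds: "These models will control for dual-task cost to serial subtraction performance (as a time-varying covariate) to isolate the costs to gait" and gives the reason: "by adjusting for potential differences in task prioritization over time".

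The dual-task assessment in section 5.1 includes a seated cognitive baseline ("Condition 1: Single task: seated cognitive task (see below for description") and dual-task standing and walking. The whole assessment is repeated at all three follow-ups, so the covariate values paired with the modelled outcomes are all post-randomisation. The sensitivity analyses described cover sex strata, baseline covariates and effect modification by age. None is an Aim 1 model that leaves this covariate out. Subtraction cost is not a listed outcome.

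**The concern.** A covariate measured after randomisation can be part of the treatment's effect. Adjusting for it then gives an arm difference at equal values of something treatment has altered, and randomisation no longer guarantees that participants compared in this way are alike.

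The documents report no tDCS effect on subtraction dual-task cost, but their reasoning makes one plausible:

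- The background attributes exaggerated dual-task costs in fallers to limited capacity: "they have a reduced capacity to activate the required brain regions needed to maintain performance in both tasks".
- It cites evidence in younger adults that tDCS over the left dlPFC "improves performance in cognitive tasks requiring attention", and extends this to dual tasking.
- Section 5.1 chose serial subtraction partly because it engages a network that includes the stimulated region, and gives participants no instruction on which task to favour. Any added capacity could go to either task.

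One limit applies. Dual-task cost is defined as a percent change ("only real tDCS reduced the dual task cost (i.e., percent change from single to dual tasking) to these outcomes"). A tDCS effect that is proportionally equal in the seated and dual-task conditions would leave subtraction cost where it was; only a differential effect moves it.

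At stake is the headline estimate of the primary aim. It could be too small or too large, and because subtraction cost is not reported by arm, the planned output would not show which.

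**Working it through.** **1. The plan's own power figure.** Inputs from Sample size determination: two-sided alpha 0.05, 57 evaluable per arm, SD 20%, serial correlation 0.75, difference 8 points. With adjustment for the baseline outcome:

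- Residual SD = 20 × √(1 − 0.75²) = 13.23.
- n per arm for 90% power = 2 × (1.960 + 1.282)² × 20² × (1 − 0.75²) / 8² = 57.5.
- Power at 57 per arm = Φ(8 / (13.23 × √(2/57)) − 1.960) = Φ(3.228 − 1.960) = 89.8%.

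The plan's statement of "90% power to detect a mean difference of 8% between intervention and control arms" therefore reproduces. The alternatives do not: no baseline adjustment gives 57.0% and a change score gives 85.5%. The figure belongs to the baseline-adjusted model without the time-varying covariate.

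**2. What the covariate does, one visit.** Two quantities are needed that the documents do not give, so both are assumptions: *d*, the fall in subtraction cost on tDCS in residual SD units, and *r*, the within-arm partial correlation between subtraction cost and motor cost. For a true total benefit of 8 points:

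Adjusted effect = 8 − r × 13.23 × d

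| d | r = +0.5 | r = +0.3 | r = −0.3 | r = −0.5 |
|---|---|---|---|---|
| 0 | 8.0 | 8.0 | 8.0 | 8.0 |
| 0.2 | 6.7 | 7.2 | 8.8 | 9.3 |
| 0.35 | 5.7 | 6.6 | 9.4 | 10.3 |
| 0.5 | 4.7 | 6.0 | 10.0 | 11.3 |

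A positive correlation shrinks the benefit. A negative one, meaning a trade-off between tasks, inflates it.

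**3. Three follow-ups, by simulation.** From the protocol: 57 per arm, SD 20%, serial correlation 0.75, three post-intervention visits. Assumed: a shift of 0, 0.1, 0.25 or 0.4 SD; r of ±0.3 or ±0.5; correlation at person level only, within visit only, or equal at both. That makes 48 scenarios, each with 1,000 trials at a true 8-point effect and 2,500 at no motor effect. The model was random-intercept GLS with arm, baseline outcome and visit, fitted with and without the time-varying covariate. It is simpler than the plan's model, which also has random slopes, sex and multiple imputation.

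Without the covariate, the estimate was 7.9 to 8.1 points and rejection with no motor effect was 4–6% throughout. With it:

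| Shift in subtraction cost | Estimate of a true 8 points | Rejection with no motor effect |
|---|---|---|
| 0 | 7.9–8.1 | 4–6% |
| 0.1 SD | 7.3–8.7 | 5–7% |
| 0.25 SD | 6.3–9.8 | 5–14% |
| 0.4 SD | 5.1–10.8 | 5–31% |

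The level at which the two costs correlate matters a great deal. At a 0.4 SD shift:

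| Correlation located | Estimate of a true 8 points | Rejection with no motor effect |
|---|---|---|
| Person level only | 7.4–8.5 | 5–6% |
| Within visit only | 5.9–10.2 | 8–17% |
| Both | 5.1–10.8 | 12–31% |

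With r = +0.5 at both levels and a 0.4 SD shift, power for a true 8 points is 75% with the covariate and 97% without it.

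**The case against.** The adjustment is deliberate, disclosed and justified. With no prioritisation instruction, a participant could lower motor cost simply by neglecting the subtractions, and the covariate is meant to deal with that. Aim 1 does not use the word total, so which contrast is primary is partly a choice of estimand. On that reading the rejection rates above are not type I errors, because the conditional contrast really is non-zero when subtraction cost has shifted.

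The large figures also need a shift of 0.4 SD, as big as the powered motor effect (8/20 = 0.4 SD), together with |r| = 0.5 at both levels. At 0.1 SD little changes, and the documents do not say which case applies. The cited cognitive evidence comes from younger adults after single sessions.

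Two points of scope remain. The stated reason mentions gait only, so the sway model may be meant to omit the covariate. The general sensitivity analyses also refer to covariates in a Section 3.3.7.3 that is not in the supplied text, so what can be said is that no Aim 1 model without the covariate is described.

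Most of this stands as a limit on how firmly the size can be put. It does not remove the gap. Prioritisation is a fair secondary question, but an arm difference at equal subtraction cost is not the effect of assignment to tDCS on dual-task cost. The 90% power also describes the other model. Nothing planned would let a reader tell a real motor effect from one created or hidden by the adjustment.

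**Conclusion.** The concern holds and should be fixed before analysis. The structural point is firm: the models that test Aim 1 condition on a variable re-measured after randomisation, the trial's rationale makes a treatment effect on it plausible, and no unadjusted comparison is described. The size is not firm. Bias is zero if tDCS does not move subtraction cost or if the two costs are uncorrelated within arm. Under the assumed shifts and correlations it runs from negligible at 0.1 SD to nearly 3 points in either direction on a true 8 at 0.4 SD. Whether the covariate is meant to enter the sway model is unclear and needs settling in any case.

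**What to change.** State one primary Aim 1 model for both sway cost and gait cost: arm, categorical visit, baseline outcome and sex, without time-varying subtraction cost. Baseline subtraction cost may be added, since it precedes randomisation. Report subtraction dual-task cost by arm and visit beside the motor costs, so that a change in prioritisation can be seen directly. Keep the time-varying-adjusted model, labelled as a supportive or exploratory analysis of task prioritisation, and say whether it covers gait only or sway as well.

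The cost is SAP wording; the seated and dual-task responses are already part of the planned assessments. The downside is that the primary estimate is no longer presented as net of prioritisation. That question is then answered from the subtraction-cost results and the supportive model.

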#### Overall approach:

Exploratory analyses will be used to assess outcomes distributions, and any necessary transformations (e.g. to combat significant skew) will be performed prior to estimation of mean treatment effects. Said estimation will use **mixed effects linear regression** of post-intervention outcomes immediately following intervention and at three and six months, with random intercepts and slopes to account for serial correlation in repeated measurements on individuals; models will control for baseline outcomes as in analysis of covariance. Owing to the potential for nonlinear trends in outcomes with time, we will assume no functional form of temporal trends. Missing data will be accommodated by multiple (at least 50) imputation of missing records using algorithms to accommodate the clustered nature of the longitudinal design. Analyses will adjust for the stratified design effect (i.e. control for sex). All estimates will be accompanied by 95% confidence intervals (CIs) for the purposes of reporting in publication. Limited hypothesis testing will be performed at the 0.05 level, but emphasis will be on estimation. Owing to the focused nature of the design and prespecification of hypotheses, no interim analyses are planned, and no significance 'adjustment' will be applied for multiplicity.

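### The Aim 1 check of change against level associates shrunken predicted intercepts and slopes, which does not estimate the true association, and the time origin is not stated

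*Combined protocol and SAP*

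**What the plan says.** Under Statistical Methods, the overall approach is a mixed model of the outcomes at three visits (immediate, three-month and six-month follow-up). The model is specified "with random intercepts and slopes to account for serial correlation in repeated measurements on individuals". Baseline enters as a covariate ("models will control for baseline outcomes as in analysis of covariance"), and for the mean over time "we will assume no functional form of temporal trends".

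The Aim 1 text under Sample size determination adds a secondary look at the random effects: "Association between model-based estimates of subject-specific intercepts and slopes (generated as random effects) will be examined". Its purpose is to assess "the degree to which change with time is associated with the average level of function denoted by each measurement".

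The documents give neither the origin of the time scale for the random slope nor the covariance structure of the random effects. They do not say that the association will be read from the estimated covariance, and they mention no allowance for shrinkage or for error shared by the two predictions.

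**The concern.** Subject-specific estimates generated as random effects are predicted values, not model parameters. Two problems follow.

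- **The predictions are not clean measurements.** Each participant's intercept and slope are computed from the same three observations and pulled together towards the mean. Their correlation mixes any true association with the geometry of the visit times and the amount of shrinkage.
- **The intercept may not be the quantity of interest.** The stated question concerns average level. If time is counted from the first post-intervention visit, the intercept is the level at that visit.

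At stake is a secondary statement about whether participants who function better or worse change differently over follow-up. It could be reported as present, absent or reversed for reasons unrelated to the participants.

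**Working it through.** **Inputs from the plan.** SD of dual-task cost 20 points ("inter-individual standard deviation of dual-task costs under either sham or intervention will be no greater than 20" percent), serial correlation 0.75, 57 evaluable participants per arm (114 in all), baseline-adjusted model, visits at 0, 3 and 6 months.

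**The plan's own figure first.** The baseline-adjusted SD is 20 × √(1 − 0.75²) = 13.23. The standard error of the difference is 13.23 × √(2/57) = 2.478, and 8/2.478 = 3.228. Power is Φ(3.228 − 1.960) = 0.898, so the stated 90% reproduces. The plan gives no figure for the intercept-slope analysis.

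**Variances given baseline** (compound symmetry):
- Between participants: 400 × 0.75 − 400 × 0.75² = 300 − 225 = 75.
- Residual: 400 × 0.25 = 100.

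**Assumption.** The documents give no slope variance. I take an SD of six-month change, g, of 1 to 15 points, so the slope variance is (g/6)² per month².

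**Formula.** Let S = 100 × (Z′Z)⁻¹ be the error covariance of one participant's least-squares intercept and slope, and D the true random-effects covariance. The predictions have covariance D(D + S)⁻¹D. If D is diagonal with elements d₁ and d₂, their correlation reduces to −s₁₂ / √[(d₁ + s₁₁)(d₂ + s₂₂)].

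**Time 0, 3, 6; first-visit level unrelated to slope.** Here s₁₁ = 83.33, s₂₂ = 5.556 and s₁₂ = −16.67, so the errors correlate at −16.67/√(83.33 × 5.556) = −0.775. For g = 6, d₂ = 1 and the predictions correlate at 16.67/√(158.33 × 6.556) = +0.52. With an origin at the last visit, s₁₂ changes sign. With centred time (−3, 0, 3), s₁₂ = 0.

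| g (points) | origin at first visit | origin at last visit | centred |
|---|---|---|---|
| 1 | +0.56 | −0.56 | 0 |
| 3 | +0.55 | −0.55 | 0 |
| 6 | +0.52 | −0.52 | 0 |
| 10 | +0.46 | −0.46 | 0 |
| 15 | +0.39 | −0.39 | 0 |

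**Time 0, 3, 6; average level unrelated to slope** (the plan's stated question). The first-visit intercept is the average level minus 3 × slope, so it is truly negatively correlated with slope: −0.06, −0.17, −0.33, −0.50 and −0.65 for the five values of g. The predictions correlate at −0.005, −0.04, −0.16, −0.37 and −0.60.

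**Estimated variances.** These are simulated null trials with n = 114, complete data and an unstructured random-effects covariance.
- Time 0, 3, 6, g = 3 to 15: mean correlation of predictions +0.15 to +0.49; 49 to 80% of trials significantly positive and 3 to 38% significantly negative.
- Centred time: the mean is near 0, but an ordinary test on the predictions rejects in about 44 to 82% of trials for g = 15 down to 6. A separate maximum-likelihood run of 300 trials per setting agrees: 38.7 + 38.0 = 77% (g = 6), 30.0 + 27.3 = 57% (g = 10) and 18.3 + 21.3 = 40% (g = 15), in either direction. The reason is that one estimated covariance shapes all 114 predictions, so its sampling error is carried into every pair.

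**The model's own parameter.** With centred time, the estimated random-effects correlation averaged −0.05 to +0.02 in simulation. For g = 6, about 21% of fits reached the boundary.

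**The case against.** A reader might infer that the plan will report a false positive association. The documents do not support that. They choose no time origin, and the stated interest in average level could be read as pointing to centred time, where the directional artefact is 0. The positive sign needs an origin before the mean visit and a null on level at that origin. Under a null on average level, the first-visit predictions correlate negatively. With an unstructured fit the positive shift is only an average tendency. All of this stands, and it removes any claim about a definite direction.

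It is also fair that no test, threshold or decision is attached to this analysis: the plan says the association will be examined and puts its emphasis on estimation. However, it also promises 95% intervals with all estimates, and an ordinary interval on this correlation would be wrong.

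One combination escapes part of the problem. With centred time and random effects forced to be independent, the ordinary test kept about its nominal size in simulation (3.7 to 5.0%). The correlation is still not the true one. It is the true value multiplied by √(75/108.33) × √(d₂/(d₂ + 5.556)), which is 0.32 for g = 6 and 0.61 for g = 15. The fitted model would also assume away the association under study.

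Finally, a reader might think that the model already delivers the wanted correlation whatever the coding. It does not: with a first-visit origin, that parameter concerns first-visit level.

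**Conclusion.** The point holds as a flaw of method with an unstated time origin. It is not a prediction of a particular wrong result. The correlation of predicted effects does not estimate the true intercept-slope correlation, and choosing a time origin does not by itself cure this.

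The +0.39 to +0.56 applies if time starts at the first post-intervention visit and level at that visit is unrelated to slope. If average level is unrelated to slope, the same coding gives about 0 to −0.60. Both ranges rest on the plan's SD and serial correlation, compound symmetry given baseline, and an assumed SD of six-month change of 1 to 15 points. The simulated rejection rates also assume complete data.

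The consequence is limited to this secondary descriptive analysis. A reader might extend the point to the treatment effects, the timepoint-specific differences or the sample size. None of these uses the predicted effects, and the 90% power reproduces.

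**What to change.** Replace the sentence on associating predicted intercepts and slopes with three commitments:

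1. Code time for the random slope as −3, 0 and 3 months, centred at the mean of the three visits, so that the intercept refers to the average over follow-up.
2. Fit an unstructured covariance for the random intercept and slope. Three visits identify it: three random-effects parameters plus one residual variance, against six distinct variances and covariances.
3. Report the REML intercept-slope covariance or correlation with its confidence interval, in place of any correlation of predicted values.

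Add that the intercept is the average level net of the model's covariates (baseline outcome, sex and the time-varying subtraction cost), so it is not raw average function.

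The cost is a short SAP edit, with no new data or visits. The downside is precision: with three visits the interval may be wide or the estimate may lie on the boundary. The SAP should say that such a result will be reported as uninformative.
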